1.2.5 Rationale for combination treatment with TMZ

TMZ is an alkylating agent that has been used in malignant gliomas of all grades. It produces *O*6-methylguanine in DNA, which mispairs with thymine during the next cycle of DNA replication. Subsequent futile cycles of DNA mismatch repair lead to a p53-associated apoptotic cell death.

[figure not shown]
A seminal study from 2005 provided level 1 evidence that the addition of TMZ to radiotherapy for newly diagnosed glioblastoma resulted in a clinically meaningful and statistically significant survival benefit.[2] Since then, TMZ has become part of standard treatment for glioblastoma. Not only used in newly diagnosed glioblastoma, TMZ has been also frequently used in grade II and III gliomas, in both upfront and recurrent settings. Clinical studies in recurrent high grade gliomas also demonstrated objective response to TMZ.[4, 36] However, the treatment effects are always limited by the resistance mechanisms, including not only MGMT expression, but also p53 and p21 status when the mismatch repair mechanism is intact.[37] In gliomas with intact p53 function, TMZ can cause prolonged cell cycle arrest and apoptosis. However, in gliomas with *TP53* mutation, TMZ induced cell cycle arrest is not sustained.[38] Zotiraciclib (TG02) not only promotes apoptosis by decreasing expression of survival proteins, such as Mcl-1, but also by regulating the cell cycle by inhibiting CDKs. This broad spectrum of mechanisms of action makes Zotiraciclib (TG02) a strong candidate to overcome resistance to TMZ treatment and subsequently lead to a prolonged response to treatment.

Figure 12: Cell viability analysis of A. GDC923; and B. U251 by using cell counting following treatment with Zotiraciclib (TG02) and TMZ alone or in combination with different sequence: Zotiraciclib (TG02) treatment for 6 hours followed by TMZ; TMZ treatment for 6 hours followed by Zotiraciclib (TG02).

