The preclinical study of cell proliferation assay from Neuro-Oncology Branch (NOB) laboratory using human-derived glioblastoma cell lines have demonstrated a significant additive effect of inhibiting tumor cell growth with combination treatment of Zotiraciclib (TG02) and TMZ. This additive effect was observed in both GSC and non-GSC cell lines (Figure 12). In *in vitro* study, GSC923 was served as a model of high grade glioma with *MGMT* promotor unmethylation and U251 was served as a model of glioma with methylated *MGMT* promotor. Cell lines with different *MGMT* promotor methylation status respond to combination treatment differently, suggesting the role of *MGMT* methylation as a stratification factor in the randomization of the clinical trials that is designed to test clinical efficacy of combination treatment of Zotiraciclib (TG02) and TMZ in high grade gliomas. Our cell-based assay also suggests that the pretreatment with Zotiraciclib (TG02) followed by a combination treatment with TMZ cause better anti-glioma effects comparing to the opposite treatment sequence. This is consistent with the hypothesis that Zotiraciclib (TG02) enhances the apoptotic effects of TMZ by suppressing the expression of anti-apoptotic proteins, which is supported by the data demonstrated in Figure 13. In Figure 13, more decreased expression of survivin, XIAP and Mcl-1 is demonstrated after combination treatment with Zotiraciclib (TG02) and TMZ, comparing to the single treatment with either Zotiraciclib (TG02) or TMZ. These anti-apoptotic proteins seem to slightly induce by TMZ treatment, which potentially contributes to the treatment resistance.

Figure 13: Western blot Western blot of survivin, XIAP and Mcl-1 in GSC923 following treatment with Zotiraciclib (TG02), TMZ alone and in combination at 8, 16, 24, and 48 hours.

1.2.6 Rationale to test Zotiraciclib (TG02) in combination with TMZ with two different dosing schedules

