Once patients with glioblastoma have recurrent disease after standard treatment defined as concurrent radiation plus daily TMZ followed by 6-12 cycles of adjuvant TMZ (150-200 mg/m² days 1-5 of a 28-day cycle), the disease is typically less responsive to TMZ. This resistance has been attributed to an increase in the tumor intracellular concentration of the enzyme O6-methylguanine DNA methyltransferase (MGMT). It has been demonstrated that if the MGMT can be depleted, sensitivity to alkylating agents such as TMZ can be restored. A study by Tolcher and his colleagues demonstrated that there was a more pronounced depletion of MGMT in peripheral blood mononuclear cells (PBMCs) after dose-intense dosing schedule of TMZ.[39] Building on this data, many studies explored the use of alternative schedules. The most notable evaluated the 7-day on – 7-day off and a metronomic schedule that used daily continuous dosing of 50 mg/m² of TMZ.

Dose-dense schedule: In a prospective study, ninety adult patients with recurrent glioma were treated with TMZ at 150mg/m²/day on days 1-7 and 15-21.[40] PFS6 was reported to be 43.8% and one-year survival rate was 23%. In contrast, another study in a similar patient population reported a PFS6 of 10% and median overall survival was 21.6 weeks.[41] Both studies demonstrated good tolerance of the treatment.

Metronomic dosing: A study of recurrent glioma patients who received metronomic TMZ at 50mg/m² yielded a PFS6 of 23.9% and a 1-year survival rate of 27.3% in recurrent glioblastoma and a PFS6 of 35.7% and a 1-year survival of 60.7% in recurrent anaplastic astrocytoma patients.[42] TMZ with both the dose-dense (dd) and metronomic (mn) schedules showed promising responses in recurrent high grade glioma patients. However, the superiority of either dosing schedule hasn't been established and comparison within the same clinical trial setting is therefore warranted.

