2.3.1 Treatment Assignment and/or Randomization/ Stratification Procedures*

Cohorts

Number	Name	Description
1	Cohort 1	Patients with recurrent anaplastic astrocytoma or glioblastoma/gliosarcoma assigned to Phase 1

2	Cohort 2	Patients with recurrent anaplastic astrocytoma or glioblastoma/gliosarcoma assigned to Phase 2
---	----------	--

Arms

Number	Name	Description
1	Phase I Arm 1	dose dense TMZ+ Zotiraciclib (TG02)
2	Phase I Arm 2	metronomic TMZ+ Zotiraciclib (TG02)
3	Phase II Arm 1	TMZ + Zotiraciclib (TG02)
4	Phase II Arm 2	TMZ (Control Arm)

Stratifications

Name	Distinct Options
KPS	Yes No
MGMT promoter methylation status of the tumor	Yes No
Presence of Measurable Disease	Yes No

In Phase I, study patients will be assigned to one of two arms to receive Zotiraciclib (TG02) plus dd TMZ or Zotiraciclib (TG02) plus mn TMZ in 1:1 ratio*. Once a phase II dose/schedule is determined, patients will be randomized to the following arms in 1:1 ratio - Zotiraciclib (TG02) plus TMZ (dose and schedule selected from phase 1 component) or Control Arm – TMZ (dosing schedule will match combination arm). Patients’ KPS, MGMT promoter methylation status of the tumors and the presence of measurable disease at study entry will be used as stratification factors.

*In Phase I, Post-interim analysis patients will be registered to cohort 1 and assigned to ARM 1, at a TG02 dose level of 200mg. Patients will be enrolled consecutively to cohort 1. Details are described in Section [3.2.1.3](#).

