3 STUDY IMPLEMENTATION

3.1 STUDY DESIGN:

3.1.1 Phase I:

The phase I component is designed to find the MTD of Zotiraciclib (TG02) in combination with 2 schedules of TMZ – dose dense and metronomic. Patients will be enrolled and equally assigned into the two dosing schedule arms for MTD finding. In each arm, the MTD will be determined independently using the Bayesian Optimal Interval (BOIN) design, fully described in Section 8 and recently published [45]. Once the MTDs of the two regimens (dd TMZ + Zotiraciclib (TG02) and mn TMZ + Zotiraciclib [TG02]) have been established, cohort expansion will be carried out at the each of the MTDs. Patients will be equally randomized into to the two cohort expansions. A post interim analysis cohort will be carried out in cohort 1 arm 1 to confirm MTD. The MTD that has higher progression-free survival rate at 4 months (PFS4) will be selected and used in phase II.

3.1.2 Phase II:

The two-arm randomized phase II will determine if the addition of Zotiraciclib (TG02) to the dd or mn TMZ schedule (determined by the expanded phase I) improves outcome in patients with recurrent malignant glioma using PFS as the primary outcomes measure. Patients will be equally randomized into the combination Arm (Zotiraciclib [TG02] plus TMZ selected from phase I) and control arm (TMZ). The randomization will stratify by the presence of measurable disease at the study entry, KPS and MGMT promoter methylation status. Additional outcomes such as PFS6, overall survival from study entry and symptom burden (using the MDASI-BT instrument in Appendix **Error! Reference source not found.**) will also be collected.

The study schema is illustrated in Study Flow Chart in Appendix 15.4.

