A randomized phase II trial will be used to compare the combination of Zotiraciclib (TG02) plus TMZ (selected from phase I) with TMZ alone in patients with recurrent grade III or IV malignant glioma. The TMZ alone arm will use the same dosing schedule as it is in the combination arm. The primary endpoint is progression free survival. We will enroll at least 10 patients and at most 40 patients for each arm at a rate of 4 patients per month. Patients will be equally randomized into two arms. Patients' KPS, MGMT promoter methylation status of the tumors and the presence of measurable disease at study entry will be used as stratification factors. We will follow all patients for at least 12 months, and monitor futility and toxicity as described below. We will use the methods described by Thall et al., to monitor progression-free survival (PFS), and we will stop enrolling patients early if, based on the available data, we have reason to believe that the median PFS of the Zotiraciclib (TG02) plus TMZ arm is less than that of the TMZ arm.^[50] Formally, we will stop enrolling patients early if

$$\Pr(\text{median PFS}_{\text{TG02+TMZ}} \geq \text{median PFS}_{\text{TMZ}} \mid \text{data from the trial}) < 0.78,$$

The futility monitoring will be conducted after enrolling 20, 40 and 60 patients (for two arms combined). Below are the operating characteristics of the above futility monitoring rule, assuming that the median PFS of the TMZ alone arm is 3 months.

Table 15 Operating Characteristics of the Futility Monitoring rule

	Median PFS for Zotiraciclib (TG02) +TMZ (months)				
	1	2	3	4	5
Early stop probability	0.999	0.812	0.374	0.170	0.097
Average sample size	23.7	42.1	62.6	70.9	74.7

Similar Bayesian methods will also be used to monitor the rate of DLT. We will monitor the two arms independently. Specifically, we will stop enrolling patients if the $\Pr(\text{DLT} > 35\% \mid \text{data}) > 0.9$. That is, we will stop enrolling patients if the data indicate that there is more than 90% chance that the true DLT rate is higher than 35%. This decision rule gives the following stopping rule, assuming a Beta (0.1, 0.4) prior distribution for DLT rate,

Stop enrolling pts if $[\# \text{ of pts with DLT}] / [\# \text{ of pts evaluated}] \geq 4/5, 6/10, 10/20, \text{ and } 15/30$.

Below are the operating characteristics of the toxicity monitoring rule.

Table 16: Operating Characteristics of the Toxicity Monitoring Rule

	True toxicity rate				
	0.2	0.3	0.4	0.5	0.6

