Early stop probability	0.014	0.096	0.345	0.716	0.939
Average sample size	39.6	37.3	31.0	21.3	13.5

At progression, patients on the control arm will be offered treatment with Zotiraciclib (TG02) in combination with continued treatment with TMZ. If an effective salvage regimen, this may impact the secondary OS endpoint, but will not affect the primary endpoint of the study. The maximum number is 80 patients.

Statistical Analysis Plan

We will use descriptive statistics to summarize the demographic and clinical characteristics of patients. We will tabulate adverse events by grade by dose level and overall. For the cohort expansion and phase II component, we will estimate the proportion of patients with response with 95% exact binomial confidence intervals, and use descriptive statistics to summarize response duration. We will estimate PFS/OS with the Kaplan-Meier product limit estimator. Log-rank test will be used to compare the PFS/OS between Zotiraciclib (TG02)+TMZ and TMZ.

Changes of symptom burden (i.e., MDASI-BT) through study time points will be assessed by paired t-tests and linear mixed model. In the mixed model, subject-specific random intercept will be used to account for within-subject correlation, and measurement time will be included as a covariate. A sample size of 40 patients has 80% power to detect an effect size of 0.454 between time points using a two-tailed test with an alpha of 0.05. The two-sample t-test and linear mixed model will be used to evaluate differences in symptom burden using the MDASI-BT between Zotiraciclib (TG02) plus TMZ and TMZ. Cox proportional hazard model will be used to evaluate the relationship between MDASI-BT and disease progression. Logistic regression will be used to evaluate the relationship between MDASI-BT and tolerance to treatment.

Treatment effects will be evaluated by advanced MRI imaging study. Perfusion and diffusion – based MRI parameters, including but not restricted to blood volume, blood flow mean and median Apparent Diffusion Coefficient (ADC) value will be analysed. Results will be summarized. The mean and median value at different time points will be tabulated. Changes in such parameters will be analysed for statistical significance and correlate with the disease status.

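### Phase II randomises within KPS, MGMT and measurable-disease strata but compares PFS by a log-rank test with no strata or covariates: essentially valid, but power is lost to the extent these factors are prognostic

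*Combined protocol and SAP*

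**What the plan says.** Stratified randomisation in phase II is stated three times. Section 3.1.2 says: "The randomization will stratify by the presence of measurable disease at the study entry, KPS and MGMT promoter methylation status". Sections 2.3.1 and 10.2 name the same three factors. The table in Section 2.3.1 gives each factor the options Yes and No, and for KPS no cut-point is stated.

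The analysis text in Section 10.2 (under Statistical Analysis Plan) estimates PFS and OS by Kaplan-Meier and then says: "Log-rank test will be used to compare the PFS/OS between Zotiraciclib (TG02)+TMZ and TMZ". The only Cox model there relates MDASI-BT scores to progression. No section supplies a stratified or adjusted treatment comparison of PFS. No significance level is given for PFS; the two-tailed 0.05 in that section belongs to the MDASI-BT calculation.

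The protocol argues that MGMT matters. Section 1.2.5 says of TMZ: "the treatment effects are always limited by the resistance mechanisms, including not only MGMT expression, but also p53 and p21 status". On cell-line data it proposes MGMT "methylation as a stratification factor in the randomization of the clinical trials that is designed to test clinical efficacy of combination treatment". Section 1.2.6 says of reduced response to TMZ after standard treatment: "This resistance has been attributed to an increase in the tumor intracellular concentration of the enzyme O6-methylguanine DNA methyltransferase (MGMT".

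**The concern.** Stratified allocation balances the arms on the stratification factors, which makes the treatment comparison less variable if those factors predict PFS. A plain log-rank test estimates its variance as if that balance had not been imposed. When the factors are prognostic, the variance it uses is therefore too large, its true false-positive rate falls below nominal, and power is lost. It also compares patients with different baseline hazards as if they were alike, which dilutes the treatment effect.

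With at most 80 patients, power is scarce. The plan may be giving up precision that it has already arranged for in the randomisation.

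**Working it through.** **1. Benchmark.** The plan states no power, target hazard ratio or event count for the PFS test, so there is no figure of its own to reproduce. Table 15 medians of 3 and 5 months give HR = 3/5 = 0.6, and 3 and 4 months give 0.75. By Schoenfeld's formula, power = Φ(|ln HR|·√d/2 − 1.96). With d = 80 events:
- HR 0.6: 0.511 × 8.944/2 = 2.285, and Φ(0.325) = 0.63.
- HR 0.75: 0.288 × 8.944/2 = 1.287, and Φ(−0.673) = 0.25.

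**2. Simulation inputs.**
- From Section 10.2: 80 patients, 1:1 allocation, 4 patients per month, at least 12 months' follow-up, control median PFS 3 months.
- Assumed, because the documents do not give them: two-sided 5% level; exponential hazards; HR 0.6 acting within strata; prevalence of low KPS 50%, unmethylated MGMT 60%, measurable disease 70%; permuted blocks of 4 in 8 cells.
- Assumed factor hazard ratios (KPS/MGMT/measurable): modest 1.25/1.5/1.25, strong 1.5/2.0/1.5, very strong 1.8/2.5/1.8.

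**3. Power at HR 0.6.** Each cell is plain log-rank versus the three-factor Cox score test with a re-randomisation p-value, in percent. The main run used 10,000 trials per setting (Monte Carlo SE about 0.5 points), or 5,000 for the MGMT-only row. Repeats A and B used 4,000 and 2,000.

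| Factors | Main run | Repeat A | Repeat B | Change (points) |
|---|---|---|---|---|
| None prognostic | 57.7 v 55.1 | 60.3 v 56.7 | 60.6 v 56.7 | -2.6 to -3.9 |
| Modest | 54.1 v 54.8 | 55.2 v 56.4 | 55.0 v 56.5 | +0.7 to +1.5 |
| Strong | 47.1 v 53.9 | 48.8 v 56.9 | 46.5 v 54.7 | +6.8 to +8.2 |
| Very strong | 40.1 v 52.9 | 39.7 v 54.5 | 41.1 v 54.2 | +12.8 to +14.8 |
| MGMT only, HR 2 | 51.9 v 55.3 | 52.4 v 56.0 | 52.5 v 55.8 | +3.3 to +3.6 |

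**4. False-positive rate (main run: none/modest/strong/very strong).** Plain log-rank: 5.6/4.9/4.0/3.0%. Re-randomised Cox: 4.8 to 5.1%. Model-based Cox: 6.1 to 6.3%, and 7 to 7.5% at 40 patients, which is why re-randomisation is preferred.

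**5. Eight-cell stratified log-rank.** Power is 51.1/50.8/50.5/49.8%. That is 4.0, 4.0, 3.4 and 3.1 points below the adjusted Cox test in the main run.

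**6. Sensitivity of the change.**
- Different inputs (prevalences 0.50/0.45/0.70, each factor HR 1.0/1.3/1.5/2.0): plain log-rank about 59/55/53/42%; Cox with model-based p-value about 59/59/61/58%.
- 60 patients: -3.4/-0.2/+5.0/+10.3 points (none to very strong). 40 patients: -4.2/-1.3/+2.4/+6.2. 20 patients: -4.4 with no factor effect, -1.1 with strong factors.
- Blocks of 2 or 6: +0.2 or +0.5 (modest), +6.4 or +6.5 (strong).
- With futility looks at 20, 40 and 60 patients: -2.5/+1.0/+7.0/+13.1. This run used a cut-off of 0.22, which approximates Table 15 (stopping 0.387 against the stated 0.374 at equal medians). The printed cut-off is 0.78.

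**7. WHO grade.** Grade is not a stratification factor, but it is the one candidate with PFS figures by group in the documents. Under exponential PFS, the hazard ratio is the ratio of log PFS6 values. Section 1.2.6 gives "PFS6 of 23.9% and a 1-year survival rate of 27.3% in recurrent glioblastoma and a PFS6 of 35.7"% in recurrent anaplastic astrocytoma (AA), so ln(0.239)/ln(0.357) = 1.39. Section 1.2.1 gives two other AA values: 31%, so ln(0.239)/ln(0.31) = 1.22, and 46% on TMZ, so ln(0.239)/ln(0.46) = 1.84. The last two are cross-study comparisons. Adding grade to the three factors changes power by -0.3 to -1.1 points at 1.22 and by +0.4 to +0.6 at 1.39. At 1.84 the change is +1.6 to +3.2 if 80% of patients are grade IV and +3.3 to +5.0 if 60% are.

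**The case against.** The case for leaving the plan alone is that this is an efficiency preference resting on assumed inputs. The test is valid, and prevalences, block size, factor strengths and the significance level are not in the documents. Under modest factors the gain is about one point at 80 patients and nil or slightly negative at 40 to 60. The very strong case needs a hazard range of 1.8 × 2.5 × 1.8 = 8.1 across patients, which nothing in the documents supports. All of this stands, and it limits the point to an inexpensive improvement.

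A reader might infer from Sections 1.2.5 and 1.2.6 that MGMT is known to be strongly prognostic here. The documents do not establish that. The evidence behind the stratification proposal is in vitro and concerns response to the combination, so it could reflect effect modification, which was not simulated. Section 1.2.6 adds that depleting MGMT can restore sensitivity to TMZ, and reports more depletion in blood cells under dose-intense dosing. Section 10.1 names the dose-dense schedule for phase II. The MGMT effect could therefore be weaker in this trial.

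Part of the loss when no factor matters is a difference in size: the plain test runs at 5.6% there. Using the same log-rank statistic with a re-randomisation p-value already costs 1.7 of the 2.6 points.

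A log-rank test stratified by MGMT alone is a simple alternative that was not evaluated.

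**Conclusion.** The point holds as a matter worth considering, with medium confidence. The mismatch between stratified randomisation and an unadjusted test is plain from the text. The direction of the effect is certain if the factors are prognostic. Its size depends on assumed factor strengths: a cost of 3 to 4 points if none matters, close to nothing if they are modest, and a gain of 7 to 15 points if they are strong or very strong.

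Three stronger readings are not supported.
- A reader might infer that the plain test inflates false positives. Its simulated size is about 5.5 to 6% with no prognostic factor, a small-sample excess unrelated to the strata, and falls to about 3% with very strong factors.
- A reader might blame the test for the low power. Power of about 55 to 60% at HR 0.6 comes from the sample size.
- A reader might take the result to hold under the futility rule as printed. The figures with interim looks apply only if 0.78 is not the cut-off that generated Table 15.

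No claim is made about OS power, because control patients may receive zotiraciclib at progression.

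**What to change.** In Section 10.2, pre-specify the primary PFS comparison as the score test for treatment from a Cox model with KPS, MGMT status and measurable disease as main effects, coded as at randomisation.
- State the KPS cut-point, which Section 2.3.1 leaves undefined.
- Take the p-value by re-randomisation within the actual allocation scheme, and record that scheme in the SAP.
- Report the adjusted hazard ratio with its 95% confidence interval, and keep the unadjusted log-rank test as a sensitivity analysis.
- Avoid the eight-cell stratified log-rank, which has less power than the adjusted test at this size.
- Decide before unblinded data are seen whether WHO grade is a fourth covariate, and name it if so. At the upper end of the implied range it gains roughly 2 to 5 points; at the lower end it gains nothing.

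The cost is a few lines of SAP text and minor programming on data already collected for randomisation, plus about 3 to 4 points of power if no factor is prognostic. A simpler fallback is the plain log-rank statistic with a re-randomisation p-value, which changes power by -1.7/-0.1/+3.7/+7.6 points from no to very strong factors.

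### The MDASI-BT arm comparison names no baseline score, so it gives up precision that a form already scheduled for every patient would supply

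*Combined protocol and SAP*

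**What the plan says.** The Statistical Analysis Plan within section 10.2 has two separate MDASI-BT analyses.

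- **Change over time.** "Changes of symptom burden (i.e., MDASI-BT) through study time points will be assessed by paired t-tests and linear mixed model". For this model, a "subject-specific random intercept will be used to account for within-subject correlation, and measurement time will be included as a covariate". The power statement that follows is within-patient and two-sided at the 0.05 level: "A sample size of 40 patients has 80% power to detect an effect size of 0.454 between time points".
- **Arm comparison.** "The two-sample t-test and linear mixed model will be used to evaluate differences in symptom burden" between the combination and TMZ alone. No model terms are listed here, and no power is given.

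Section 10.2.1 treats the registration questionnaire as baseline, says that data received after randomization enter the primary analyses, and includes every patient with at least one valid form. It does not say whether the baseline score is a covariate, an outcome row or unused.

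The baseline form is required by section 2.4.4, section 3.4.1 and the study calendar (3.8). On phase II size, section 10.2 says "We will enroll at least 10 patients and at most 40 patients for each arm" and "Patients will be equally randomized into two arms".

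**The concern.** A patient's symptom score before treatment usually predicts the score afterwards. When that score is already collected, a randomized comparison that ignores it carries avoidable noise. A t-test on follow-up scores ignores it entirely. A t-test on change scores uses it less efficiently than a covariate does. The plan does not say which outcome the t-test takes.

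There is a second, conditional risk. If the arm model reused the change-over-time structure, baseline rows could enter as outcomes. With arm only as a main effect, the arm term would then average over a visit at which no treatment effect can exist.

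The number of follow-up forms matters. Forms come at imaging visits every two cycles (8 weeks), and section 10.2 assumes a control median PFS of 3 months. Many patients may therefore supply only one or two. Longitudinal MDASI-BT evaluation is a secondary objective (1.1.2.3).

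**Working it through.** **Inputs from the documents.** 40 per arm at most and 10 at least, 1:1 allocation (10.2); two-sided alpha 0.05; n = 40 and effect size 0.454 for the paired statement (Statistical Analysis Plan).

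**Inputs assumed, not in the documents.** Correlation ρ between baseline and follow-up of 0.4 to 0.6; SD 2 points; true arm difference 1 point, so d = 1/2 = 0.5; complete data.

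**1. The plan's own figure.** For a paired t-test, df = 39 and noncentrality = 0.454 × √40 = 2.87. Power from the noncentral t is 79.96%, so the stated 80% reproduces. It does not describe the arm comparison. For two arms of 40 at the same d, noncentrality = 0.454 × √(40/2) = 2.03, and power is 51.8%.

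**2. Standard error of a single-visit arm contrast.**

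- Unadjusted: SD × √(2/n) = 2 × √(2/40) = 0.447.
- Adjusted for baseline: multiply by √(1 − ρ²).

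| ρ | √(1 − ρ²) | Adjusted SE | Reduction |
|---|---|---|---|
| 0.4 | 0.917 | 0.410 | 8% |
| 0.5 | 0.866 | 0.387 | 13% |
| 0.6 | 0.800 | 0.358 | 20% |

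If the t-test were run on change scores, its variance would be 2(1 − ρ) times that of follow-up scores. The adjusted-to-change SE ratio is then √((1 + ρ)/2) = 0.837, 0.866 and 0.894. Adjustment still cuts the SE, by 11 to 16%.

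**3. Power at one follow-up, d = 0.5.** The effect is d unadjusted and d/√(1 − ρ²) adjusted.

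| Per arm | Unadjusted | ρ = 0.4 | ρ = 0.5 | ρ = 0.6 |
|---|---|---|---|---|
| 40 | 59.8% | 67.4% | 72.2% | 78.8% |
| 10 | 18.5% | 21.2% | 23.1% | 26.3% |

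At 40 per arm and ρ = 0.5 the gain is 72.2 − 59.8 = 12.4 points.

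**4. The conditional case.** Take K follow-ups, balanced data, a random intercept, arm as a main effect and no arm-by-time term. With the baseline row kept as an outcome, the arm coefficient averages K visits carrying the effect and one carrying none, so it estimates K/(K + 1) of the true value. Power is for 40 per arm, d = 0.5, ρ = 0.5, from three variances in units of SD²:

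- baseline row kept: (1 + Kρ)/(K + 1), with effect d × K/(K + 1);
- post-baseline rows only: (1 + (K − 1)ρ)/K;
- post-baseline rows with baseline covariate: the previous line minus ρ².

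| K | Share of effect kept | Baseline row kept | Post-baseline only | With baseline covariate |
|---|---|---|---|---|
| 1 | 50% | 24.7% | 59.8% | 72.2% |
| 2 | 67% | 43.8% | 72.2% | 87.8% |
| 3 | 75% | 55.4% | 77.2% | 92.8% |

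A simulation of 200 trials with K = 2, ρ = 0.6 and true d = 0.5 gave mean estimates of 0.32, 0.49 and 0.49 in the same column order, consistent with the 2/3 factor.

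**The case against.** **The time-only model is not the arm model.** A reader might infer that the plan compares arms in a mixed model whose only covariate is time. The documents do not say so. The sentence naming time follows the change-over-time analysis and precedes a within-patient power figure. The arm model's terms are never listed, not even arm. This stands: the defect is that the arm model is unspecified and names no baseline.

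**Dilution is not the planned analysis.** A reader might also infer that the planned arm estimate is biased towards zero. Section 10.2.1 leans the other way, since it sets registration forms apart as baseline and refers to data received after randomization. It is not decisive. Its rule of including anyone with one valid form would let a baseline-only patient in, which makes sense only if baseline can be an outcome. The same paragraph opens with responders against non-responders, not arms. Setting the diluted column against the fully adjusted column would therefore overstate the gain. The relevant contrast is post-baseline unadjusted against adjusted, about 12 to 16 points.

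**The inputs are assumed.** This stands. Section 10.2.1 sets the meaningful difference at 2 points. With SD 2 that is d = 1, and 40 per arm already gives 99.3% power unadjusted, leaving almost nothing to gain. At 10 per arm the same difference gives 56.2% unadjusted and 68.5% with ρ = 0.5. Dropout also lowers every figure. If losses followed a 3-month median before week 8, 40 × 2^(−1.84/3) ≈ 26 per arm would remain, and power at d = 0.5 would be 42.4% unadjusted and 53.3% adjusted.

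**Randomization protects the unadjusted contrast.** It does, apart from dropout. Without dilution the cost is precision, not bias.

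**Conclusion.** The concern holds as a loss of precision in an under-specified secondary analysis. For ρ of 0.4 to 0.6, adjusting for baseline lowers the SE of a single-visit contrast by 8 to 20%. At 40 per arm with a 1-point difference, SD 2 and ρ = 0.5, power at one follow-up goes from about 60% to about 72%. The direction does not depend on the SD or the effect size. The size does, and it also depends on a correlation that the documents do not give and on reaching the maximum enrolment.

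Shrinkage to K/(K + 1) is a risk to be closed by wording, not a property of the plan as written. The primary PFS analysis is untouched.

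**What to change.** In the Statistical Analysis Plan of section 10.2, write out the arm model and replace the two-sample t-test with a baseline-adjusted contrast at each visit. Either of two forms will do:

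- a mixed model of post-baseline scores with baseline score, arm, visit and arm-by-visit; or
- a constrained longitudinal model in which baseline is an outcome but both arms share one baseline mean, with arm effects only at later visits.

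The first drops patients who lack a baseline form or any follow-up form, which conflicts with section 10.2.1's rule of including anyone with one valid questionnaire. The second keeps them and so fits that rule. Section 10.2.1 should also state the role of the baseline form, and the 0.454 statement should be labelled as within-patient only.

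The cost is plan wording. No new visits, forms or patients are needed.
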